Lofexidine for Rapid Opioid Tapering in Adults

NCT04126083

12/30/2019

Lofexidine for Rapid Opioid Tapering in Adults

A. BACKGROUND

Lofexidine has recently been approved by the U.S. Food and Drug Administration (FDA) for mitigation of opioid withdrawal symptoms in order to facilitate abrupt or tapered opioid discontinuation in adults. One potential use of the compound is in situations where rapid detoxification (partial or complete) is desired, such as impending surgery. Lofexidine (racemic mixture of R-/+ and S-/-enantiomers, dexlofexidine and levlofexidine, respectively) is a full alpha-2 receptor agonist.(1-5) However, lofexidine is pharmacologically distinct from other alpha-2 agonists, such as clonidine whose use has previously been described for the treatment of opioid withdrawal syndrome (OWS). (6-8)

Concerns about OWS are major deterrent for patients on opioid therapy, often hampering success and compliance with opioid tapering regimens.(9-11) Fortunately, amelioration of such negatively experienced signs and symptoms may be accompanied by improved patient outcomes. Lofexidine was originally approved as a pharmacologic agent for opioid detoxification in the United Kingdom and other countries, including much of the European Union, starting in the 1980s. Studies have demonstrated efficacy in the amelioration of OWS with fewer adverse effects and a better safety profile than clonidine.(12, 13) Specifically, lofexidine has a lower incidence of hypotension than clonidine, making it more suitable for the management of OWS in outpatient settings.(12) Additionally, unique from clonidine, lofexidine also binds to 5-HT_{1A} (i.e. serotonin) receptors. As serotonin levels decrease during periods of withdrawal from opioids,(14) compounds with 5-HT_{1A} agonism could potentially be beneficial in combatting OWS. As an example, a compound with 5-HT_{1A} agonist properties was recently shown to decrease withdrawal symptoms in opioid-dependent mice. (15, 16) Hence, activity mediated through 5-HT_{1A} receptors may help explain additional benefit of lofexidine for OWS treatment beyond that of simple alpha-2 agonism.

In a recently published multicenter phase III randomized controlled trial of more than 600 patients dependent on opioid therapy, lofexidine at doses of 2.16 and 2.88 mg/day significantly reduced OWS versus placebo.(17) Additionally, lofexidine increased the rate of completing the 7-day period of 'abrupt discontinuation' by 14% and 12% for the 2.16 and 2.88 mg/day dosing groups, respectively. Hence, lofexidine has the potential to serve as a withdrawal treatment option when non-opioid agents are preferred or required or when opioid agonist-assisted withdrawal is unavailable. Additionally, lofexidine may potentially be used to manage withdrawal symptoms that occur during induction or maintenance treatment with mixed opioid agonists and antagonists.

With increased attention on a widespread national problem of opioid misuse and abuse, recently declared a national Public Health Emergency by the U.S. Department of Health and Human Services, medical practices in the U.S. are trying to shift towards more conservative approaches to pain management with less reliance on opioids as first-line therapy. Consistent with this, recent guidelines released by the Centers for Disease Control and Prevention (CDS) endorse avoidance of opioid therapy to the greatest extent possible for chronic pain states.(18) However, chronic opioid use remains a significant national problem. Data from acute pain and postoperative states suggests that patients taking opioids preoperatively, especially at high doses, have poorer outcomes than those not taking opioids.(19-29) This includes heightened risk for immediate postoperative outcomes such as infection, ileus, and respiratory depression and longer-term complications such as poor wound healing and decreased success rates following spinal fusion.(30) Moreover, patients on opioids preoperative typically require higher doses and durations of opioid therapy postoperatively and generally consume more health care

resources than their opioid-naïve counterparts.(19, 21, 31-35) Given these findings, a drug that facilitates reliable, safe, and rapid detoxification or partial detoxification may be particularly beneficial for patients on chronic opioid therapy preparing to undergo a planned surgical procedure. Patients presenting for elective spine surgery are at particularly high risk for chronic preoperative opioid use,(34) and hence, this group may particularly benefit from targeted approaches to wean opioids preoperatively.

Specific aims

Specific Aim 1: The primary objective is to investigate the effects of lofexidine in adults (N=25) undergoing opioid tapering. In this phase 4 clinical trial, an open label, variable dose design will be used to facilitate opioid tapering during a 15-day period. The primary outcome measure of this study is the number of patients who discontinue opioid use at day 15.

Specific Aim 2: Secondary aims include investigating the effects of lofexidine on the severity of OWS, pain intensity, negative affect, and opioid craving following completion of the 15-day study period. Secondary outcome measures will include the Clinical Opiate Withdrawal Scale, the Short Opiate Withdrawal Scale-Gossop, the numerical pain rating scale, Center for Epidemiologic Studies-Depression scale, the Pain Catastrophizing scale, and a composite scale of opioid craving.

Specific Aim 3: This exploratory aim will investigate the change in heat pain perception attributed to changes in opioid induced hyperalgesia. Prior to the opioid taper and on day 15, quantitative sensory testing will be conducted using the Computer Aided Sensory Evaluator IV (WR Electronics, Stillwater, MN).

B. PROCEDURES AND METHODS

B.1. Study Site

The study will be conducted at the medical (e.g., pain clinic, pain rehabilitation center) and surgical (e.g., orthopedic and spine surgery clinics) clinics at Mayo Clinic Rochester, MN. All patients will be recruited from the medical and surgical clinics at Mayo, and all assessments and follow-up will be conducted in the pain clinic and pain rehabilitation center.

B.2. Study Design

B.2.1. Study methodology

A prospective, open label, single center, variable dose design will be used to investigate the effects of lofexidine in adults undergoing a 15-day taper. The primary outcome will be the number of subjects who discontinue opioid use at day 15.

B.2.2. Opioid tapering

Following informed consent, the baseline opioid dose will be reduced 5% to 50% based on the physician investigators clinical discretion and patient acceptability of the dose reduction. The physician investigators will reassess each patient for further opioid dose reductions (5% to 50% allowed) in the pain clinic or pain rehabilitation center on study days 3, 6, and 9. On all other study days, patients will be contacted by telephone by study personnel to assess for OWS and adverse effects related to lofexidine use.

Prior to initiating the opioid taper, the physician investigators will contact the physician or provider responsible for prescribing long-term opioid therapy. During the 15-day study period, the physician investigators will assume full prescribing authority, and patients and their established prescribers will be asked to halt the provision of all opioid prescriptions during the study period. Upon completion of the study, the physician investigators will contact the

established long-term prescriber to ensure continuity of care with the provision of ongoing prescriptions.

B.2.3. Variable lofexidine dosing

Upon initiation of the opioid taper, patients will receive oral lofexidine 0.54 mg 4 times daily (3 tablets of 0.18 mg 4 times daily) for a total daily dose of 2.16 mg. The variable dose design will allow the lofexidine dose to be increased up to 0.72 mg 4 times daily (4 tablets of 0.18 mg 4 times daily) by the physician investigators if OWS are elevated. The lofexidine dose may also be reduced by the physician investigators to 0.18 mg 4 times daily) to relieve adverse effects attributed to lofexidine.

On study days 10 through 15, equal quantities of the baseline lofexidine dose will be reduced, and lofexidine will be discontinued on day 15. All patients will be contacted within 24 hours of study completion to assess for any residual or late emerging adverse effects.

B.2.4. Heat pain perception

Prior to opioid tapering and on day 15, quantitative sensory testing will be conducted using the automated Computer Aided Sensory Evaluator IV (CASE IV; WR Medical Electronics, Stillwater, MN) system based on the method of levels. The CASE IV system delivers a series of short duration heat stimuli of variable magnitude interspersed with null stimuli in random order through a thermode with surface area of 10 cm². The validated HP test algorithm takes less than 5 minutes to complete. This protocol includes the standardized test procedures, stimulus waveform, null stimulus, and non-repeating stepping algorithm between the different levels of heat stimuli. The subject is masked to each level of stimulus delivered, including the null stimulus. Immediately after the stimulus is given, the subject then rates the stimulus intensity on an 11-point rating scale (0 denotes no pain, 10 denotes the most intense possible pain). The test is completed when either the maximum stimulus has been delivered, or when the subject grades the stimulus intensity ≥ 5.

In total, there are 25 different magnitudes of heat stimuli, expressed in units termed "just noticeable difference" (JND). The heat stimuli magnitude of each level is comprised of 2 elements: (1) temperature, and (2) duration of exposure. The baseline temperature is 34°C and the thermal rise rate is 4°C/second. There is an exponential increase in the temperature and the thermode reaches 48°C at level 21 for a duration of 1 second. For levels 22, 23, and 24, the temperature remains at 48°C for a duration of 1.5, 5, and 10 seconds, respectively. The maximum heat stimulus is level 25, which is comprised of a temperature of 49°C for a duration of 10 seconds. Higher temperatures are not used in order to avoid thermal tissue injury.

The CASE IV software program (WR TestWorks, version 2.0) adjusts the raw sensory data, recorded in units of JND, to account for age, sex, height, weight, body surface area, body mass index, and body region of testing.(36-38) Then, a quadratic regression equation is fitted to the pain ratings, and the CASE IV software calculates HP 0.5, HP 5, and HP 5-0.5. The midpoint between a nonpainful stimulus and the least stimulus magnitude necessary to elicit a threshold sensation of pain is termed HP 0.5. The stimulus magnitude necessary to elicit a pain rating of 5, indicating intermediately intense pain, is labeled HP 5. HP 5-0.5 is named the pain-stimulus response slope and signifies the difference between HP 5 and HP 0.5.

The testing conditions will be consistent between patients. The anatomical site selected for testing (due to ease of accessibility) will be the dorsal surface of the non-dominant hand. If the non-dominant hand is an anatomical site of pain, then the dominant hand will be used.

B.2.5. Postoperative opioid use

For surgical patients, immediate preoperative opioid dose and pain scores will be assessed upon admission to the preoperative area. Opioid dose and pain scores will be reassessed upon hospital dismissal and at day 30 (+/- 5 days) following lumbar spine. The preoperative and hospital dismissal assessments will be performed by members of the study team, and the day 30 assessments will performed via telephone.

B.3. Study Participants

B.3.1. Inclusion criteria

- 1. Age 18 to 70 years.
- 2. Chronic pain for \geq 3 months duration.
- 3. Daily morphine equivalent dose between ≥ 20 mg.

B.3.2. Exclusion criteria

- 1. Cancer-related pain.
- 2. Medical or surgical conditions that could be adversely impacted by opioid tapering or use of lofexidine including, but not exclusively limited to, cardiac disease, inflammatory bowel disease, renal or hepatic impairment, vascular disease, and history of anaphylaxis. Patients may be excluded for other comorbid medical or surgical conditions based on the physician investigator's discretion.
- 3. History of schizophrenia or other chronic psychiatric disorder that could be adversely impacted by opioid tapering or use of lofexidine. Patients may be excluded for other comorbid mental health conditions based on the physician investigator's discretion.
- 4. Neurological condition that impair functioning in an ambulatory setting or could be adversely impacted by opioid tapering or use of lofexidine including, but not exclusively limited to, Parkinson's disease, amyotrophic lateral sclerosis, or a dementing illness. Patients may be excluded for other neurological conditions based on the physician investigator's discretion.
- 5. Active substance abuse disorder.
- 6. Inability to function in an ambulatory care setting due to severe deconditioning requiring use of supportive gait aids including a cane or walker. Patients may be excluded for other functional problems based on the physician investigator's discretion.
- 7. History of adverse effects attributed to opioid tapering or lofexidine use.
- 8. Use of medications from drug classes known to have adverse interactions with lofexidine including, but not exclusively limited to, beta-blockers, calcium channel blockers, alpha 1 and 2 receptor antagonists, tricyclic antidepressants, benzodiazepines, and selective serotonin reuptake inhibitors. Patients may be excluded for use of other medications based on the physician investigator's and research pharmacy's discretion.

B.4. Sample Size

The primary aim of this study is to assess the effects of lofexidine on opioid tapering in adults. The purpose of this open label study is to decide whether additional studies using an experimental design are warranted, and to provide preliminary data for designing a larger efficacy trial. The primary outcome will be the number of subjects who discontinue opioids at day 15. We anticipate opioid discontinuation will be observed in 50% to 70% of patients. Thus, a sample-size of N=25 will be sufficient to assess whether additional studies of lofexidine in this patient population are warranted.

B.5. Data Collection and Assessments

B.5.1. Demographics and clinical characteristics

Baseline demographic and clinical characteristics will be collected including age, sex, race and ethnicity, marital status, work status, educational status, pain diagnosis, pain duration, smoking status, use of non-opioid medications, previous spine surgery history or other non-spine surgery, and indication for current surgery.

B.5.2. Determination of morphine equivalent dose

The daily opioid dose of each patient will be determined by self-report and review of pharmacy and medical records. Using a software program available at our institution, the daily opioid dose will be converted to an oral morphine equivalent dose expressed in milligrams (mg) per day.

B.5.3. Opioid tapering

The primary outcome measure of this study is the number of patients who discontinue opioids at day 15.

B.5.4. Pain intensity

Pain intensity will be assessed using the 11-point numerical pain rating scale (NRS). The validity of the NRS has been well established.

B.5.5. Negative affect

Depressive symptoms and pain catastrophizing are key components of negative affect. The Center for Epidemiologic Studies-Depression scale provides a validated measure of depressive symptoms in patients with chronic pain. The Pain Catastrophizing Scale provides a measure of negative cognitions and emotions associated with actual or anticipated pain experiences.

B.5.6. Opioid craving

Opioid craving will be assessed using responses (0 to 100 VAS) to 3 questions: (1) How much do you crave opioids? (2) How often do you think about the next dose? (3) How strong is your urge to take more medication than prescribed? This approach has been used to assess craving in patients with chronic pain.

B.5.7. Heat pain perception

Heat pain perception will be quantified using the Computer Aided Sensory Evaluator IV (WR Electronics, Stillwater, MN). This QST device has been validated, and we have used it to quantify opioid-induced hyperalgesia and to study other pain-related states associated with altered heat pain perception.

B.5.8. Signs and symptoms of opioid withdrawal

The severity of opioid withdrawal symptoms will be assessed using two measures. First, the Clinical Opiate Withdrawal Scale (COWS) is an observer-rated instrumaent. Total score range from 0 to 47. Scores ranging from 5-12 denote mild withdrawal symptoms, scores from 13-24 signify moderate withdrawal, scores from 25-36 indicate moderately severe symptoms, and scores greater than 36 indicate severe withdrawal symptoms. Second, the Short Opiate Withdrawal Scale-Gossop (SOWS-Gossop) is a subjective score provided by the subject. It includes 10 items assessed by the patient as none/not present (0 points), mild (1 point), moderate (2 points), or severe (3 points).

B.5.9. Lofexidine adverse effects

According to previous reports, common adverse effects associated with lofexidine include orthostatic hypotension, hypotension, bradycardia, insomnia, somnolence, sedation, dry mouth, syncope, and tinnitus. Management of adverse effects is described in the Human Subjects section.

B.5.10. Urine toxicology screening

The opioid status of all patients will be biochemically verified with a confirmed urine toxicology screen prior to the opioid taper and at day 15.

B.5.11. Timeline of patient assessments

Screening visit (at least (7) days before baseline assessment)

Screen for inclusion and exclusion criteria.

Obtain informed consent.

Obtain urine toxicology screen and ECG.

Day 1 (baseline)

Informed consent reviewed and documented.

Physical examination performed, vital signs documented.

Determine opioid dose reduction.

Start lofexidine.

Obtain baseline assessments.

Day 3+3 days (pain clinic follow-up with physician investigator)

Physical examination performed, vital signs documented.

Determine opioid dose reduction.

Assess for opioid withdrawal and lofexidine adverse effects.

Lofexidine dose adjustment if indicated.

Day 6 +3 days(pain clinic follow-up with physician investigator)

Physical examination performed, vital signs documented.

Determine opioid dose reduction.

Assess for opioid withdrawal and lofexidine adverse effects.

Lofexidine dose adjustment if indicated.

Day 9 + 3 days (pain clinic follow-up with physician investigator)

Physical examination performed, vital signs documented.

Determine opioid dose reduction.

Assess for opioid withdrawal and lofexidine adverse effects.

Lofexidine dose reduction initiated.

Day 12 to 15 (pain clinic follow-up with physician investigator)

Physical examination performed, vital signs documented.

Assess for opioid withdrawal and lofexidine adverse effects.

Determine opioid new baseline dose.

Lofexidine discontinued.

Obtain day 15 assessments.

Days 1-15 (telephone assessment)

Daily telephone call to assess for opioid withdrawal, pain, and lofexidine adverse effects.

B.6. Data Handling

The working database will be maintained on a secure institutional server. All computer files and systems will be password protected and accessible by authorized study personnel only. Data entry will be performed by the research coordinator.

B.7. Data Analysis

Demographics (e.g., age, sex, marital status, educational status, employment status), and clinical characteristics (e.g., pain duration, depression, pain intensity) will be summarized. Mean and standard deviation will be calculated for continuous variables, and count and proportion will be calculated for categorical variables. The primary outcome measure will be the number of patients who discontinue opioid use at day 15. In the analysis of secondary aims, nonparametric paired tests will be used to assess for differences in pre- and post-taper scores of opioid withdrawal, pain intensity, negative affect, and heat pain perception. The frequency of all lofexidine adverse effects will be documented. Perioperative opioid use and pain scores will be summarized.

B.8. Strengths and Limitations

At the conclusion of this project, we will have investigated the effects of lofexidine in adults undergoing opioid tapering. These data will be critical to the design of a future efficacy trial of lofexidine in this patient population.

All study participants will be recruited from the medical and surgical clinics at a tertiary referral medical center. As a result, the study findings may not be applicable to all adults undergoing elective lumbar spine surgery.

References

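### Section B.5.11 lets the day 15 status be taken from day 12, although the primary outcome, urine screen and heat pain test are fixed at day 15

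*Combined protocol and SAP*

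**What the plan says.** All references are to the combined protocol and SAP.

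- **Endpoint day.** Specific Aim 1 and sections B.2.1, B.4, B.5.3 and B.7 define the primary outcome at day 15. B.2.4 puts the second heat pain test on day 15. B.5.10 calls for a "confirmed urine toxicology screen prior to the opioid taper and at day 15". None of these gives a window.
- **Opioid reductions.** After the first reduction, B.2.2 has the physician investigators reassess for "further opioid dose reductions (5% to 50% allowed) in the pain clinic or pain rehabilitation center on study days 3, 6, and 9". It continues: "On all other study days, patients will be contacted by telephone".
- **Lofexidine.** B.2.3 reduces it over days 10 to 15 and stops it on day 15.
- **Visit timeline (B.5.11).** The last visit that lists an opioid reduction is headed "Day 9 + 3 days (pain clinic follow-up with physician investigator". The next and final clinic visit is headed "Day 12 to 15 (pain clinic follow-up with physician investigator". Its items include "Obtain day 15 assessments" and the stopping of lofexidine.
- **Calls (B.5.11, days 1 to 15).** "Daily telephone call to assess for opioid withdrawal, pain, and lofexidine adverse effects".

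**The concern.** The study has one primary result, a count at a single time point. The outcome statements fix that time point at day 15, but the table that staff will follow allows it to be recorded on day 12, 13, 14 or 15. Two patients with the same opioid history could then be classified differently because of their appointment dates.

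The time since the last scheduled reduction would also vary between patients. That matters for the secondary pre/post comparisons of withdrawal, pain and heat pain in B.7, because the final scores would be taken at differing distances from the last change in opioid dose.

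B.4 says the study is meant to show whether further studies are warranted and to supply preliminary data for a larger trial. A discontinuation rate that mixes day 12 and day 15 status is a less clear planning figure than one tied to a single day.

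**Working it through.** The plan states no interval between the last reduction and the endpoint, so there is no figure of its own to reproduce. The check sets the days side by side.

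**Inputs**

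| Item | Text sections | B.5.11 |
|---|---|---|
| Last scheduled opioid reduction | day 9 (B.2.2) | days 9 to 12 |
| Day 15 assessments | day 15 (Aim 1, B.2.1, B.2.4, B.5.3, B.5.10) | days 12 to 15 |
| Lofexidine stopped | day 15 (B.2.3) | days 12 to 15 |
| Sample size | 25 (B.4) | – |

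**Step 1. Nominal interval.** 15 − 9 = 6 days for every patient.

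**Step 2. How early the endpoint can be taken.** 15 − 12 = 3 days.

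**Step 3. Interval allowed by the table.** Longest: 15 − 9 = 6 days. Shortest: 12 − 12 = 0 days. B.5.11 states no minimum gap between the two visits.

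**Step 4. Sensitivity to the printed plus sign.** If the heading was meant as plus or minus 3 days, the last reduction visit runs from day 6 to day 12. The interval is then 12 − 12 = 0 to 15 − 6 = 9 days. Day 12 remains the latest reduction day, so the two windows still meet.

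**Step 5. What is observed on days 13 to 15 if the final visit is on day 12.**

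- B.5.11 lists no later clinic visit.
- Its daily calls cover withdrawal, pain and lofexidine adverse effects. The calls in B.2.2 cover withdrawal and lofexidine adverse effects. Neither lists opioid use.
- The contact within 24 hours of completion in B.2.3 concerns adverse effects.
- B.5.2 determines opioid dose from self-report and records but names no day.
- B.5.10 sets a urine screen at day 15. B.5.11 names a urine screen only at the screening visit, so it does not say whether the final screen belongs to the day 12 to 15 visit or is a separate collection on day 15.

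So if the screen is taken together with the day 15 assessments on day 12, no scheduled contact on days 13 to 15 lists opioid use. If it is a separate collection on day 15, that gap is at least partly closed, but the table provides no visit for it.

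**Step 6. Weight of one patient.** 1/25 = 4 percentage points. For scale, the exact (Clopper-Pearson) 95% interval is 31% to 72% at 13/25 (52%) and 47% to 85% at 17/25 (68%). Both observed rates lie inside the 50% to 70% that B.4 anticipates.

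**The case against.** The best defence is that B.2.2 and the outcome statements give nominal days while B.5.11 gives working visit windows. That is fair for the reductions: an allowance of 3 days around day 9 is ordinary and on its own a mild inconsistency. It is less persuasive for the endpoint, because the window runs only early, and no outcome statement allows for it. A reader could take the final heading as a span with the endpoint items kept for day 15, but the table does not say so.

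The impact is also limited. One patient is 4 points against a 95% interval roughly 40 points wide, the study has a single arm, and B.4 sets no success threshold. No changed decision can be shown.

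Several stronger readings are tempting, and the documents do not support them:

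- *Opioid use on days 13 to 15 goes unobserved.* Not as a general statement. B.5.10 does set a urine screen at day 15, and B.2.2 gives the investigators full prescribing authority for the 15 days. The gap arises only if the screen is taken at the earlier visit.
- *The plan schedules the last reduction and the endpoint on the same day.* It permits this on day 12, as the boundary of two separately listed visits. It does not plan it, and the documents do not show how often it would occur.
- *A reduction close to the urine sample biases the count downwards.* That needs a rule for a positive screen in a patient whose recorded dose is zero, and none is stated.
- *The final visit brings another opioid change.* The item "Determine opioid new baseline dose" can equally mean recording the post-taper dose for the usual prescriber, and no reduction is listed at that visit.

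**Conclusion.** The inconsistency is real and should be fixed. The primary outcome, urine screen, heat pain test and lofexidine stop are set at day 15 without a window, while B.5.11 places the day 15 assessments and the lofexidine stop at one visit on any of days 12 to 15. Status can therefore be taken up to 3 days early, and 0 to 6 days after the last scheduled reduction instead of 6.

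The consequence for the primary result is conditional. If the urine screen goes with the other assessments at a day 12 visit, a patient who resumes opioids on days 13 to 15 could still be counted as a success. Each such patient adds 4 percentage points. The number of patients affected cannot be derived from the documents, and neither can a net direction of error across all patients.

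The conclusion assumes that staff follow B.5.11 as printed. The possible early assessment and the day 12 overlap hold whether the day 9 window is read as plus 3 or as plus or minus 3 days.

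**What to change.** Reconcile B.5.11 with B.2.2, B.2.3 and the primary outcome. Which days the opioid and lofexidine reductions fall on is for the investigators to state; this review takes no position on them.

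For measurement only:

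1. Take the primary-outcome opioid status and the final urine screen in a window that opens on day 15 and has a stated closing day, before prescribing returns to the usual prescriber. Without a closing day, the window could pick up opioid use outside the study period. Name the urine screen in the corresponding B.5.11 entry.
2. Add opioid use since the last contact to the daily call already planned for days 1 to 15.
3. Report the number of days from last opioid reduction to endpoint for each patient.

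The cost is a short amendment to the timeline, one more question on an existing call and one more reported variable. No extra patients are needed. The downside is less scheduling freedom: some patients seen on days 12 to 14 may need one more visit.

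### Heat pain (Aim 3): time since the last opioid dose is neither controlled nor recorded, so the paired change cannot be attributed to hyperalgesia alone

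*Combined protocol and SAP*

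**What the plan says.** Specific Aim 3 states its purpose as follows: "This exploratory aim will investigate the change in heat pain perception attributed to changes in opioid induced hyperalgesia". B.2.4 sets the two occasions: "Prior to opioid tapering and on day 15, quantitative sensory testing will be conducted". It standardises the stimulus procedure and then says "The testing conditions will be consistent between patients". The site "will be the dorsal surface of the non-dominant hand", with one exception: "If the non-dominant hand is an anatomical site of pain, then the dominant hand will be used". The software adjusts the raw data "to account for age, sex, height, weight, body surface area, body mass index, and body region of testing"; drug timing and side of the body are not in that list.

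B.7 plans paired tests of a nonparametric kind, looking at "differences in pre- and post-taper scores of opioid withdrawal, pain intensity, negative affect, and heat pain perception". The comparison is therefore each patient against themselves, with no covariates.

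Three other sections bear on drug state at the two tests:
- **B.3.1** requires at least 20 mg of morphine equivalent per day at entry.
- **B.4** expects 50% to 70% of patients to have discontinued by day 15.
- **B.5.2** captures the daily opioid dose, but not when the last dose was taken.

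**The concern.** In a paired analysis, what matters is that conditions match between one patient's two tests. Here one important condition, the amount of opioid acting at the time of testing, differs systematically between them. At baseline every patient is on opioids, tested at an unspecified interval after a dose. At day 15 more than half may have none on board.

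Two effects then pull in opposite directions. If hyperalgesia recedes, a stronger stimulus is needed to produce pain, so HP 0.5 and HP 5 rise. If acute analgesia was present at baseline and is gone at day 15, they fall. The paired difference is the net of the two. With a single arm there is no control group to separate them, and dose times that were never recorded cannot be recovered later.

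At stake is the reading of an exploratory result. B.4 says the study is to supply preliminary data for a larger trial. A flat or reversed change could be taken as evidence that hyperalgesia did not recede, when it may only reflect the timing of the baseline test.

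**Working it through.** **Plan's own figure.** The only stated size is N=25, tied to the primary outcome. No alpha, power, effect size or SD of change is given for heat pain, so there is nothing to reproduce. What follows is an illustration.

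**Inputs from the documents:** n = 25 pairs (B.4); proportion off opioids at day 15, p = 0.50 to 0.70 (B.4), that is 25 × 0.50 = 12.5 to 25 × 0.70 = 17.5 patients.

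**Assumptions:** two-sided alpha 0.05; no dropout; true rise from receding hyperalgesia of 0.5 SD of the paired change; loss of acute analgesia worth 0.25 SD in those affected.

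**Formula.** Mean net change in SD units: d = 0.5 − 0.25 × (fraction affected). Power comes from the noncentral t distribution with 24 degrees of freedom and noncentrality d × √25 = 5d.

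| Who carries the offset | d | 5d | Power |
|---|---|---|---|
| Nobody | 0.5 | 2.5 | 0.670 |
| Discontinuers, p = 0.50 | 0.5 − 0.125 = 0.375 | 1.875 | 0.437 |
| Discontinuers, p = 0.70 | 0.5 − 0.175 = 0.325 | 1.625 | 0.345 |
| All 25 | 0.25 | 1.25 | 0.225 |

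The discontinuer rows keep the SD at 1. They treat patients still on a reduced dose as carrying no offset, which is favourable to the plan, so the truth under these assumptions would lie between those rows and the last one.

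**Check with the type of test planned.** B.7 specifies nonparametric tests. A simulated two-sided Wilcoxon signed-rank test (25 normal paired differences, 4,000 runs per case, assumed true change 0.6 SD) shows the same pattern when the offset applies to everyone: power 0.81 with no offset, 0.56 with a quarter of the change offset, 0.29 with half, and 0.05 with all of it.

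**Hand rule.** A switch of hand has no expected direction; it adds a side-to-side difference to that pair. In the same simulation, extra noise of 0.5 SD in every pair lowers power from 0.81 to 0.72. A switch would affect only the few pairs in which it occurred, so its effect should be smaller than that.

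**The case against.** **Conditions are already standardised.** B.2.4 fixes the procedure, waveform, null stimulus, stepping algorithm and site, and these hold for every test, so also within patient. A reader might infer from the sentence on consistency between patients that the sponsor means to let conditions vary within a patient. The text does not support that. What remains is narrower: the patient's drug state is not among the things standardised or recorded.

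**The size is unknown.** This stands. The direction is plausible, but the documents say nothing about how much acute analgesia shifts heat-pain values in long-term users. An assumed offset as large as the assumed effect cancels it by construction and proves nothing. Nor should the full offset be applied to all 25 patients without comment, since 30% to 50% are expected to be still on opioids at day 15.

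**The hand rule is probably meant to be applied once.** This largely stands. In patients with pain of at least 3 months' duration, whether a hand is a painful site reads naturally as a settled characteristic, and a switch needs hand pain to appear or resolve within about 15 days. A reader might put the hand rule on a par with the dose-timing problem; it is only a small possible source of noise.

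**Timing cannot be matched in patients who have stopped.** This also stands. A baseline test just before a usual dose is not an opioid-free test, and patients who take opioids as needed may have no usual dose time.

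**Dose times may be kept in a test procedure or on a form.** Possibly, but none is mentioned, and Aim 3 makes an attribution that depends on them.

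**Conclusion.** The concern holds in a limited form. As written, the plan yields a net change in heat pain that mixes loss of acute analgesia with any change in hyperalgesia, and it collects nothing that would help to tell them apart. The attribution in Aim 3 is therefore stronger than the design supports.

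Under the assumptions shown (0.5 SD effect, 0.25 SD offset, 25 pairs, paired t), power falls from 67% to about 34% to 44% if only discontinuers are affected, and to 22% if all are. These figures show sensitivity, not expected loss. It would go too far to say that the acute effect will cancel or reverse the change, or that the problem can be fully avoided: the documents give no magnitude, and better timing reduces the offset without removing it.

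This is a worthwhile improvement to an exploratory aim. The primary outcome, discontinuation at day 15, is untouched.

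**What to change.** Amend B.2.4 and B.7, without changing any dosing:

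1. Where a patient has a regular opioid schedule, book the baseline heat test shortly before a usual dose, and in all patients before the first lofexidine dose. The day 1 list in B.5.11 puts starting lofexidine ahead of the baseline assessments and does not say whether that is the intended order.
2. At both tests, record hours since the last opioid dose, hours since the last lofexidine dose, and the hand used.
3. Use the baseline hand at day 15 unless it has become painful; if it has, flag the pair. This keeps the existing protection against testing a painful site.
4. Report the paired change overall, by opioid status at day 15, and without pairs that depart from these rules.
5. State that the change is a net effect of receding hyperalgesia and lost acute analgesia, which timing can reduce but not remove.
6. Reconcile the day 15 test in B.2.4 with the final visit in B.5.11, which is headed day 12 to 15.

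The cost is tighter scheduling on day 1, a few form fields and some wording; no test is added. For as-needed opioid users the time since the last dose can only be recorded, not planned. The breakdown by opioid status will rest on small groups (about 12 to 18 discontinuers on the plan's own expectation) and should be descriptive.
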